Our preliminary work has focused on airway management of critically ill patients who require MV. We found that development of VAP is associated with up to \$40K per case in additional costs, along with longer LOS.^{13,112} Our work has identified that frequency of oropharyngeal suction varies widely, and that the tonsil suction device is preferred.²⁶⁻²⁸ In a simulated laboratory setting, we determined that the oropharyngeal suction catheter was more effective than either a suction swab or tonsil suction device in removing oropharyngeal secretions.⁹⁹ Two oropharyngeal suction catheters are included in oral care kits used on MV patients at the study site to be used concurrently with tooth brushing; however, average use is only 0.8 per day.⁹⁵ Many patients have large volumes of oropharyngeal secretions that can be potentially aspirated.^{25,93,113} In preliminary work, we suctioned an average of 7.5 mL of secretions within a 4-hour interval, although volumes as high as 25 mL were removed.²⁵ Secretion removal can be achieved with ≤ 3 suction passes with the oropharyngeal suction catheter over an average total duration of 48.1 seconds.²⁵ We have not identified any issues when using the oropharyngeal suction catheter.^{25,93} *In a recent pilot study of 13 critically ill subjects, we found that all subjects had α -amylase present in the oral secretions, and 6 (46%) had α -amylase detected in the first tracheal sample.⁹³ The study was done to test α -amylase procedures and the intervention. A second specimen obtained one to four hours later (when ETT suctioning was needed) showed only 4 subjects (31%) with α -amylase in the tracheal secretions, and a lower value in those positive.* The study established our ability to measure α -amylase in the APH Specialty Diagnostic Laboratory with precision and quality controls. It also provided data that microaspiration frequently occurs in our study population and may be reduced with this simple intervention. Our co-investigator, [name], has studied biomarkers for microaspiration.¹¹⁴⁻¹¹⁸ He also provides oversight for the laboratory, including developing the procedures for quantifying α -amylase. These multiple preliminary studies informed our decision to focus on enhanced removal of oral secretions, using an oropharyngeal suction catheter, on a 4-hour schedule, with α -amylase as our primary outcome measure.

Design

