A prospective, 2-group, single-blind, randomized clinical trial design is planned. The design will allow us to test the impact of the NO-ASPIRATE intervention on outcomes of microaspiration and VAC.

Aims and Hypotheses

Our primary aim is to compare the effects of the NO-ASPIRATE intervention versus usual care on microaspiration in critically-ill intubated patients on MV. Patients often have high volumes of oropharyngeal secretions, and despite existing interventions, microaspiration occurs. Regular removal of secretions that accumulate in the oropharynx is intended to decrease the volume or potential load, and thus reduce microaspiration. Our working hypotheses are that subjects in the NO-ASPIRATE group will have a reduction in microaspiration as measured by the percentage of tracheal specimens that are positive for α -amylase (1.1) and *mean values of α -amylase* (1.2).

A secondary aim is to compare the effects of the NO-ASPIRATE intervention on development of VAC and duration of VAC-free days. By reducing the risk for microaspiration, VAC should be reduced. Our working hypotheses are that the subjects in the NO-ASPIRATE group will have a lower rate of VAC (2.1) and longer duration of VAC-free days (2.2). Another secondary aim is to explore changes in the ratio of α -amylase in the tracheal aspirate versus the mouth over time. Our working hypothesis is that subjects in the NO-ASPIRATE group will have a lower tracheal/oral α -amylase ratio over time (3.1).

Setting and Sample

Setting. The study will be conducted in the ICUs at Orlando Regional Medical Center (ORMC), a division of Orlando Health. ORMC is an 808-bed tertiary care facility that specializes in trauma, emergency care, cardiology, orthopedics, neurosciences, and internal medicine. The hospital serves a 5-county area in Central Florida area with a diverse population of 2.8 million people.¹¹⁹ The ICUs include Trauma (14 beds), Neuroscience (16 beds), Multi-System (10 beds), and Cardiac (10 beds). Nursing and respiratory care practices for airway management are standardized across units. The patients are managed by a team of either

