Randomization. Our biostatistician will oversee the process of randomization of subjects to either the NO-ASPIRATE or usual care group. He will develop a blocked randomization procedure, using different sized blocks, to ensure balanced assignment without being able to predict group assignment.¹⁶⁶ Because many subjects will be intubated with the specialized SS-ETT (about 65% from historical data), we will stratify randomization by type of ETT to ensure that approximately half of those with and without the SS-ETT are randomly assigned to each group. Stratification will help to address type of tube as a potential confounding variable, and will allow for secondary sub-group analysis. A member of the study team not involved in data collection will place group assignments for each type of ETT in numbered, sealed, opaque envelopes. Upon enrollment, study personnel will identify the type of ETT, and open the appropriate envelope to determine group assignment. Only study team members who provide the intervention will know the subjects' assigned groups. ICU personnel, as well as subjects and family members, will be blinded to the assignment.

Intervention. Following enrollment, the RA will collect baseline data, implement the assigned intervention (NO-ASPIRATE or usual care/sham), and collect specimens. The RA will then implement the intervention as designated by study arm every 4 hours. *Figure 4 summarizes the procedures for each group.*

To control for possible differences in usual oral care practices, the RA will perform oral cleansing and suctioning with a suction swab after delivering the NO-ASPIRATE or sham intervention using the hygiene components from the oral care kit. The RA will also perform tooth brushing every 12 hours. Oral antisepsis will be done after obtaining specimens for α -amylase. Some subjects may require additional oral suctioning for secretion management; staff will use the available tonsil suction device for oral suctioning in-between the scheduled interventions and document in the medical record. Additional necessary oral suctioning will be recorded and controlled for, if applicable.

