Outcome: Microaspiration; % tracheal specimens positive for α -amylase; mean value of α -amylase in tracheal secretions	Assays of α -amylase in tracheal aspirate	Enrollment Every 12 hours Duration: up to 14 days while intubated	Aim 1—Microaspiration
Outcome: Ventilator-Associated Condition (VAC)—yes/no Subset: Infection-Related Possible VAP Probable VAP	Medical record data: 
• Ventilator: PEEP, FiO_2• Temperature• WBC / culture results• New antibiotics / duration	Daily Assess for 2 days beyond the last intervention	Aim 2—VAC
Outcome: Ratio of α -amylase in tracheal and oral secretions	Assays of α -amylase from paired tracheal and oral specimens	Enrollment Every 12 hours Duration up to 14 days	Aim 3—tracheal/oral ratio of α-amylase
Demographic Data			
ETT information (time of intubation, type ETT, size ETT)	Observation Medical Record	Enrollment	Describe sample Stratify by ETT type
Age, gender, ethnicity, diagnoses	Medical Record	Enrollment	Describe sample Compare groups
Comorbidities: COPD; immune-compromise; chronic heart, liver, or renal failure	Medical Record	Enrollment	Describe sample Compare groups
Acuity and outcomes: APACHE II, APACHE IV, SAPS, ventilator days, LOS	Hospital database	Completion of participation in study	Describe sample Test group equivalence
Physiological status: vital signs, oxygen saturation, sedation level	Medical Record	Enrollment Daily (am)	Describe sample Test equivalence
Potential Risk Factors for Microaspiration and VAC			
Backrest elevation (daily average)	Observation	Every 4 hours	Test equivalence
GI data: tubes, nutritional support; gastric residual, distention; vomiting	Medical Record Observation	Enrollment Daily (am)	Test equivalence
ETT: min, max, mean daily cuff pressure; repositioning; cuff issues	Medical Record	Daily	Test equivalence
Oral care: additional interventions, type of antiseptic	Medical Record Intervention documentation	Daily	Test equivalence
GI medications: H_2 blockers, proton pump inhibitors, antacids, sucralfate	Medical Record	Enrollment Daily (am)	Test equivalence
Mobility and transport off unit	Medical Record/observation	Every 4 hours	Test equivalence

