Paired specimens of oral and tracheal aspirates for α -amylase. The RA will obtain an oral specimen for α -amylase at enrollment and every 12 hours (concurrently with a tracheal aspirate) to compute the tracheal/oral ratio. Oral secretions will be collected into a trap during the NO-ASPIRATE or usual care/sham intervention. Following this procedure, a tracheal aspirate will be obtained for detection of α -amylase. Although Weiss detected α -amylase in BAL specimens up to 72 hours post intubation, others have suggested more frequent collection.^{46,97} Obtaining specimens every 12 hours will provide longitudinal data regarding microaspiration, and facilitate identification of clinical factors that contribute to its occurrence. The RA will suction the subject's ETT per standard procedure (closed ETT suction with hyperoxygenation via the ventilator before the procedure) to retrieve tracheal secretions into a specimen trap. We tested these procedures in a preliminary study.⁹³ Since ETT suctioning should be done based on identified need,¹²¹ the RA will assess the subject for cues identifying suctioning need before obtaining the specimen: audible crackles over the trachea, sawtooth

pattern on the ventilator flow waveform, cough, high peak inspiratory pressure, visible secretions, or changes in oxygen saturation.^{85,122} *If suctioning is not indicated at the scheduled time, the RA will collaborate with the subject's nurse to notify the RA if suctioning is clinically indicated within a 2-hour period to ensure complete collection of samples. Time of specimen collection (or omissions) will be noted. The usual care oral antisepsis done for all subjects will be done AFTER specimen collection to prevent contamination.* All oral and tracheal specimens will be frozen to -20° C until the assays are run. A compact medical lab freezer, used solely for purposes of this study, will be purchased and located on or near one of the study units for easy storage. Specimens will be regularly transported on ice to the APH Specialty Diagnostic Laboratory.

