Microaspiration. Assays of the biomarker, α -amylase, in paired oral and tracheal specimens will be performed in the APH Pediatric Specialty Diagnostic Laboratory per standard procedures (See Appendix A). Laboratory personnel will be blinded to study group. Alpha-amylase activity in the paired samples will be analyzed using the Stanbio α -amylase LiquiColor Reagent Kit. The recommended procedure was modified for a microplate reader. Each run of samples is accompanied by two controls, and the controls are evaluated before results are released. A 10 μ l sample is placed in a microplate well, and 200 μ l of α -amylase LiquiColor reagent, which has been pre-warmed to 37°C, is added to each sample and mixed. The increase in absorbance is measured at 405nm in a spectrophotometer in 3-minute intervals for 9 minutes. The average change in absorbance is used to calculate a standard curve of α -amylase in μ mol/min/ml, which will be converted to U/L. *An α -amylase value of 0.6 μ mol/min/ml will be considered positive. No amylase should be detected; the value 0.6 μ mol/min/ml is the lowest possible concentration of amylase that can be detected with the method's analytic sensitivity. After detection, the total values of α -amylase in secretions will be recorded. Amylase that is detected would be either of oropharyngeal or gastrointestinal origin; however, in this setting and location of sampling, presence from pancreatic source would be unlikely. Indeed the additional step of using a specific inhibitor for salivary amylase was shown to be not necessary in airway samples during our preliminary study. The paired oral-tracheal samples evaluated in the preliminary study detected large amounts of α -amylase in the oral secretions of all subjects, and smaller amounts in those who also had positive results in tracheal secretions.*⁹³

To address Aim 1 and hypothesis 1.1, total values of α -amylase will be recorded, and each tracheal aspirate will be coded as either positive or negative for α -amylase. [name], also blinded to study group, will verify the results of each assay. The percentage of positive specimens for the biomarker will be calculated for each subject. For hypothesis 1.2, the mean values of α -amylase will be calculated.

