Subjects will be randomly assigned to each of the two treatment groups at 1:1 ratio. Before analysis, data will be carefully examined for accuracy. Every effort will be made to avoid missing data. Subject characteristics at baseline will be examined to ensure a sound balance on demographic variables between the two groups. For continuous demographic variables, independent two-sample *t* tests will be used to detect differences between the two groups. For categorical demographic variables, the Pearson's chi-square test will be used to examine differences between the two groups. If subject subsets are found to be significantly different for a demographic variable, then this variable will be included into the statistical models. All planned analyses will be based on the intent-to-treat (ITT) population, which consists of all subjects who have been randomized into the NO-ASPIRATE or usual care group. In all analyses, an alpha level of 0.05 will be used.

[figure not shown]

Figure 6. Algorithm for Determining VAC

Aim 1. To compare the effects of the NO-ASPIRATE intervention versus usual care on microaspiration of gastric and oral contents in critically-ill intubated patients. Hypothesis 1.1.

Subjects in the NO-ASPIRATE group will have a significantly lower percentage of tracheal secretions with α -amylase present as compared to those in the usual care group. **Analysis 1.1.** Percentages of tracheal secretions α -amylase present for both groups will be computed. The percentage difference between the two groups will be calculated along with the 95% confidence interval for the percentage difference. The logistic regression including covariates of interest will be used to assess the percentage difference adjusting for the prognostic covariates.

Hypothesis 1.2. Subjects in the NO-ASPIRATE group will have a lower mean value of α -amylase in tracheal secretions as compared to those in the usual care group. **Analysis 1.2.** Values of α -amylase in tracheal secretions will be collected for each subject every 12 hours during study. Treatment effect based on these values over time will be evaluated by the generalized linear models using the generalized estimating equation (GEE) method.^{124,125} In addition, the generalized linear models with prognostic covariates of interest will be used to assess change in mean values of α -amylase over time adjusting for prognostic covariates.

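### The H1.1 percentage positive counts the enrolment tracheal specimen, taken after only one assigned procedure, so the primary arm difference is diluted by an amount that depends on length of stay

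*Combined protocol and SAP*

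**What the plan says.** Table 1 gives the collection times for the Aim 1 tracheal outcome as "Enrollment Every 12 hours Duration: up to 14 days while intubated". In the Microaspiration paragraph of the measurement section, "each tracheal aspirate will be coded as either positive or negative", and then "The percentage of positive specimens for the biomarker will be calculated for each subject". Neither that paragraph nor Analysis 1.1 leaves out the enrolment specimen or gives it another role. Human Subjects, parts A and B, describe the same specimen as baseline.

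The order of events at enrolment is set in two places. The Intervention section has the research assistant collect baseline data, then "implement the assigned intervention (NO-ASPIRATE or usual care/sham), and collect specimens". The section on paired oral and tracheal specimens says "Following this procedure, a tracheal aspirate will be obtained for detection of" the biomarker. If suctioning is not indicated at the scheduled time, the same section lets the tracheal specimen be taken when the need arises within the next 2 hours.

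The mechanism is stated under Aims and Hypotheses: "Regular removal of secretions that accumulate in the oropharynx is intended to decrease the volume or potential load".

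For H1.2, the Microaspiration paragraph refers to mean values. Analysis 1.2 says "Treatment effect based on these values over time will be evaluated by the generalized linear models" fitted by GEE, without saying whether the enrolment value is a response, a covariate or left out.

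**The concern.** The intervention is a schedule of suctioning repeated every 4 hours. At enrolment one procedure has been done, usually moments before the tracheal specimen and at most about 2 hours before it. A specimen taken then can show little of what the running schedule does, yet it carries the same weight in a subject's percentage as any later specimen. If its expected arm difference is smaller than that of later specimens, the average is pulled toward zero.

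The pull is strongest in subjects with few specimens. The primary estimate would then depend partly on how long patients stay intubated, and would be smaller than the effect of the schedule once it is running.

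**Working it through.** **Inputs.** From Power Analysis: 400 analysed subjects (taken as 200 per arm), a 15% reduction, alpha .05, power .87. From Preliminary Studies: 46% positive in the first pilot tracheal sample and 31% in one taken 1 to 4 hours later, 13 subjects. From Sample: ventilation median 4 days, mean 6.2 days. From Endpoints: 36-hour minimum for analysis and 14-day limit. The documents give neither the distribution of stay nor the effect of a single procedure, so both are assumed below and varied.

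**1. The plan's own figure.** Take 46% v 31%, 200 per arm, two-sided .05. The pooled rate is .385.
- Null SE = √(2 × .385 × .615/200) = .0487.
- Alternative SE = √((.46 × .54 + .31 × .69)/200) = .0481.
- Power = Φ((.15 − 1.96 × .0487)/.0481) = .872, matching .87.

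The 15% is therefore absolute points. Use of the pilot rates is inferred from this match; the plan does not state the H1.1 rates.

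**2. Dilution for one subject.** With a specimen at enrolment and every 12 hours, k = 1 + hours/12, rounded down. If a fraction f of the effect is present at enrolment, the expected difference is 15 × (1 − (1 − f)/k). Worst case, f = 0:

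| Stay | k | Enrolment share | 15 points reads as |
|---|---|---|---|
| 36 h | 4 | 25% | 11.3 |
| 4 days | 9 | 11% | 13.3 |
| 14 days | 29 | 3% | 14.5 |

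**3. Dilution over a mix of stays.** Assume a lognormal stay with median 4 and mean 6.2 days, so σ = √(2 ln(6.2/4)) = .936. Keep stays of at least 36 hours, cap at 14 days and ignore tracheostomy.
- Mean 1/k = .115, mean k = 12.7, median k = 10; about 10% of subjects have k = 4.
- Per-subject average: 15 × (1 − .115) = 13.3.
- Pooled specimens: 15 × (1 − 1/12.7) = 13.8.
- Gamma or Weibull stays with the same median and mean: about 13.5 per subject and 14.0 pooled.
- With an assumed tracheostomy time added to the lognormal model: about 13.1 per subject.
- With f = .25, .5 or .75: 13.7, 14.1 or 14.6 per subject.
- If everyone randomised is analysed, as Data Analysis says, with no 36-hour rule and enrolment 0, 12 or 24 hours after intubation: 12.5, 11.8 or 11.4 per subject at f = 0.

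**4. Power.** Simulation with a probit random intercept, 400 subjects, 46% v 31% after enrolment, no effect at enrolment, the stays of step 3, and a z test on per-subject proportions:

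| Latent correlation | Enrolment counted | Enrolment excluded |
|---|---|---|
| 0 | 1.00 | 1.00 |
| .3 | 1.00 | 1.00 |
| .5 | .99 | 1.00 |
| .7 | .96 | .98 |
| .9 | .88 | .95 |
| .99 | .82 | .90 |

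Repeat runs differ by a point or two. Under the null, rejection was .053 with either definition. Analysis 1.1 specifies group percentages and logistic regression rather than this z test, so the table is a guide. In the one-binary-per-subject calculation of step 1, a 13.3-point difference gives about .78.

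**The case against.** The strongest reply is that the enrolment specimen is a legitimate randomised outcome. It follows assignment and one assigned procedure, and Data Analysis bases every analysis on all subjects randomised. Counting every specimen after assignment is a coherent definition. This stands: the definition is valid. It estimates a smaller quantity than the effect of the running schedule, and the plan does not say that it meant to choose that quantity.

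A reader might also infer that the specimen is untreated. The collection order does not support this. Because of the 2-hour allowance, some enrolment specimens could even fall within the interval at which the pilot saw its lower rate. The no-effect figures are therefore a worst case. Nor does the pilot settle the matter: 13 subjects, before and after, without a control group, cannot show that a first specimen is a clean pre-treatment value.

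Finally, the loss is modest. Under the 36-hour rule and the stay models used, the worst-case shortfall is about 1.0 to 1.9 points of 15. At latent correlation .5 the per-subject lognormal shortfall of 1.7 points is about half the simulated standard error of 3.1 points. That is fair, and it limits the severity.

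**Conclusion.** The point holds for H1.1. As written, the percentage includes the enrolment specimen, and the expected arm difference is pulled toward zero unless one procedure already gives the full effect. The best single figure is 15 points reading as about 13.3 per subject or 13.8 pooled with no effect at enrolment, and about 14.1 per subject with half the effect present. These figures rest on the assumed stay distribution, on specimens collected on schedule, and on an effect that is constant after enrolment.

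Three stronger readings are not supported. First, the primary test is not invalid: the arms are randomised, the pull is toward the null, and type I error is unchanged. Second, power does not collapse. The loss is about 0 to 3 points up to latent correlation .7 and about 6 to 8 points at .9 to .99, and the documents give no correlation with which to choose. Third, no error is shown in the 1.2 GEE. Its treatment of the enrolment value is unstated, so dilution there is possible but not established.

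Severity: minor to moderate.

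**What to change.** - In the Microaspiration paragraph and Analysis 1.1, define the H1.1 percentage, and any simple H1.2 summary mean, on tracheal specimens collected after enrolment (12 hours onward).
- Report the enrolment results separately, by arm.
- For consistency, state that the responses in the 1.2 GEE are the post-enrolment values.
- Do not use the enrolment tracheal result as a baseline covariate. Under the written order it is collected after the first assigned procedure and may already carry part of the effect. The plan does not propose this adjustment, but its covariates are unnamed and the baseline label invites it.
- Report by arm the number of subjects with no post-enrolment specimen.

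This removes the dilution due to the enrolment specimen. It removes all dependence on stay only if the effect is complete by 12 hours and constant afterwards; if benefit builds over days, early later specimens dilute too.

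The change is wording only and leaves collection as it is. The cost is that subjects with no later specimen contribute no Aim 1 outcome. By stay alone that is none under the 36-hour rule, and about 1% to 8% in the lognormal model if all randomised subjects are analysed. Specimens missed because suctioning was not needed add to this.
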